6.1.6 Interim Analyses and Data Monitoring

There is no formal interim analysis planned.

The primary analysis will take place once all Week 24 data have been entered, cleaned and evaluability has been finalized.

To meet the trial's ethical responsibility to its subjects, results will be monitored by a Data Safety Monitoring Board (DSMB) that has no formal involvement with the subjects or the investigation. The DSMB will be comprised of two clinicians with expertise in dermatology and/or EB and a statistician. The DSMB will facilitate the management and identification of potential safety concerns that could affect the safety of study subjects and will evaluate the

overall progress of the study. To minimize risk, cumulative safety data will be reviewed by the DSMB. Principal investigators (PIs), additional Sub-Is and scientific personnel may participate in reviews, as appropriate.

The DSMB has the authority to recommend dose or regimen modifications for safety concerns and will provide recommendations about stopping or continuing the trial. To contribute to enhancing the integrity of the trial, the DSMB may also formulate recommendations relating to the selection/recruitment/retention of subjects, their management, improving adherence to protocol-specified regimens and retention of subjects, and the procedures for data management and quality control.

Details regarding the DSMB, procedures, responsibilities, membership, meeting intervals and data to be evaluated are further described in the study specific DSMB Charter. A written summary documenting the results and recommendations of each DSMB meeting will be maintained on file with the Sponsor.

6.1.7 Multicenter Studies

The clinical study will be conducted under a common protocol for each investigational site with the intention of pooling the data for analysis. Every effort will be made to promote consistency in study execution at each investigational site. Primarily because of the small sample size of the trial, analyses will not formally test for any difference between effects by center.

6.1.8 Multiple Comparisons/Multiplicity

No multiplicity adjustments will be implemented due to exploratory nature of comparisons.

6.1.9 Use of an Efficacy Subset of Subjects

No efficacy subsets will be summarized.

6.1.10 Active-Control Studies Intended to Show Equivalence

Not applicable to this study.

6.1.11 Examination of Subgroups

Not applicable to this study.

6.2 Disposition of Subjects

The number of subjects included in each analysis population (randomized, FAS, safety) will be summarized. The number of subjects randomized, completed, and discontinued (including the

reasons for discontinuation) will be summarized. The number of randomized wounds per subject will also be summarized.

Subjects who are excluded from an analysis population will be summarized by the reasons for exclusion.

6.3 Protocol Deviations

Protocol deviations will be evaluated as per the clinical database and additionally tracked by operational study team members. Protocol deviations will be summarized according to category and a by-subject listing of all protocol deviations will be presented.

6.4 Data Sets Analyzed

Subjects will be summarized based on the primary reason for exclusion.

6.4.1 Randomized Population

All subjects who are randomized to study treatment will be included in the randomized population. Listings and summaries will be provided for all randomized subjects.

6.4.2 Full Analysis Set (FAS)

All subjects in the randomized population who are administered FCX-007 will be included in the FAS. The primary efficacy analysis will be performed using the FAS.

In the case that a Standard of Care (SOC) wound is inadvertently injected with FCX-007, then the primary efficacy analysis will consider this wound in the SOC group (as randomized) as per the intent-to-treat philosophy.

If any treated wounds from the second or third pairs are not able to be fully treated for any reason, then these wounds will not be included in efficacy analyses beyond the timepoint they were not able to be treated, i.e., Day 1 or Week 12.

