9. TREATMENTS

9.1. TREATMENTS ADMINISTERED

All target wounds (treatment and control wounds) should receive same standard of care wound dressings. Routine skin care for subjects will continue throughout the study.

FCX-007 will be administered intradermally at Day 1 (Visit 2) and Week 12/Month 3 (Visit 3) to the treatment wound(s) only. FCX-007 may also be administered at Week 24/Month 6 (Visit 4) and Week 36/Month 9 (Visit 5) to unclosed treatment wounds and unclosed control wounds, per the investigator's discretion.

At selected clinical study sites only, in a subset of subjects that consent to additional research skin biopsy collection, an additional single treated wound (not from a target wound pair) may be injected with FCX-007 at Day 1 (Visit 2) and Week 12/Month 3 (Visit 3) only.

The IP provided is for use only as directed in this protocol.

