10.3. ANALYSIS POPULATIONS

10.3.1. Full Analysis Set

The primary population for analysis of efficacy is the full analysis set (FAS). The FAS population includes subjects who were administered FCX-007.

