5.1.2 Secondary Efficacy Endpoints

The secondary efficacy endpoints are as follows:

- Complete wound closure of the First Wound Pair at Week 12
- Complete wound closure of all wounds at Week 24
- Complete wound closure of all wounds at Week 12

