6.7.5 Sensitivity Analyses

Sensitivity analyses will be included in order to assess the impact of missing data.

In the event of missing Week 24 WAs (with confirmatory closure at Week 22) for either wound, sensitivity analyses will consider these wounds as failures.

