8. CHANGES IN THE PLANNED ANALYSES

Due to changes in sample size, originally planned formal analyses of primary and secondary endpoints analyses are now descriptive. In addition, the Per-Protocol population and associated analyses have been removed.

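### SAP 6.4.2 excludes Second- and Third-pair treatment wounds that were not fully treated but leaves their paired controls in, so the all-wounds percentages by arm can rest on different pairs

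*SAP*

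**What the plan says.** The rule is in SAP 6.4.2. Treatment wounds of the Second or Third Pair that "are not able to be fully treated for any reason, then these wounds will not be included in efficacy analyses" are removed from the session at which treatment fell short, which the section identifies as Day 1 or Week 12. The wounds removed are the treatment wounds; neither 6.4.2 nor any other SAP section says what happens to the matched control.

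Protocol 9.1 explains why the rule can act on one arm only: "FCX-007 will be administered intradermally at Day 1 (Visit 2) and Week 12/Month 3 (Visit 3) to the treatment wound(s) only".

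Two of the three secondary endpoints in SAP 5.1.2 pool all pairs: "Complete wound closure of all wounds at Week 24" and its Week 12 counterpart. SAP 6.7.2 reports them as counts and percentages by treatment group and does not require complete pairs. SAP 6.7.3 adds durability and pain summaries over all wounds, including a maximum pain score across wounds.

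On sensitivity, SAP 6.7.5 says that where the Week 24 assessment is missing "for either wound, sensitivity analyses will consider these wounds as failures". SAP section 8 records that formal analyses became descriptive and that "the Per-Protocol population and associated analyses have been removed"; it does not mention the wound-level exclusion.

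**The concern.** Each pair was formed so that its two wounds would be comparable, and one was then randomised to treatment. If the treatment wound leaves the summary and its control stays, that comparability is lost for the pair, through a post-randomisation event that can occur in one arm only.

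The documents give several reasons why a wound might not be fully treated:
- shortage of product (Protocol 9.7, SAP 4.1);
- withholding because of inflammation suspected to be product-related, or unusual growth (Protocol 9.7);
- a positive pregnancy test (Protocol Table 3, footnote 8, and 8.4.4.3);
- suspension of administration for safety (Protocol 7.6.1);
- discontinuation of administration while assessments continue (Protocol 7.6.2).

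Some of these can be events after the first injection, even responses to it. With no test or model planned, the two percentages side by side are the reported comparison, so what they are computed over matters.

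**Working it through.** **The plan's own figure.** The plan gives no figure for this rule. Its only design calculation is 85% power with 24 pairs (SAP 7). An exact two-sided McNemar calculation, with discordant pairs Binomial(24, 0.70) and conditional probability 0.60/0.70, gives 85.1%, so it reproduces. It served the original formal analysis and does not bear on the all-wounds summaries.

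**Which results are reached.** The exclusion applies "these wounds will not be included in efficacy analyses beyond the timepoint they were not able to be treated". Closure is assessed before any injection at the visit (SAP 4.1.3). Hence:
- a Day 1 shortfall removes the wound from all-wounds closure at Weeks 12 and 24;
- a Week 12 shortfall removes it from Week 24 onward, not from Week 12;
- First Wound Pair endpoints are outside the rule;
- durability is reached less, because its qualifying wounds are already limited to those assessed as closed.

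**Is a shortfall plausible?** One session's maximum is expected to cover about 60-80 cm² (SAP 4.1), and each wound may be up to 50 cm². Three treatment wounds exceed that cover when their mean area is above 60/3 = 20 to 80/3 = 26.7 cm²; two exceed it above 60/2 = 30 to 80/2 = 40 cm². This shows that shortage is possible, not how often it occurs.

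**Illustrative size.** Six subjects with three pairs each give at most 6 × 3 = 18 wounds per arm; with two pairs each, 6 × 2 = 12. Assume no true effect, overall closure p = 10% in both arms, and shared prognosis within pairs. Let m treatment wounds be dropped, with closure rate d among them. The rate in the kept treatment wounds is

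k = (N·p − m·d) / (N − m), and the shift in the arm difference is k − p.

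| N | m | d = 0 | d = 10% | d = 15% |
|---|---|---|---|---|
| 18 | 1 | 1.80/17 = 10.6%, +0.6 | 0 | 1.65/17 = 9.7%, −0.3 |
| 18 | 3 | 1.80/15 = 12.0%, +2.0 | 0 | 1.35/15 = 9.0%, −1.0 |
| 18 | 6 | 1.80/12 = 15.0%, +5.0 | 0 | 0.90/12 = 7.5%, −2.5 |
| 12 | 1 | 1.20/11 = 10.9%, +0.9 | 0 | 1.05/11 = 9.5%, −0.5 |
| 12 | 3 | 1.20/9 = 13.3%, +3.3 | 0 | 0.75/9 = 8.3%, −1.7 |

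Removing both wounds of each affected pair gives k − k = 0 under the same assumptions.

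**Other assumed inputs.** Take 30% closure in retained pairs and 10% in affected pairs, both arms, with 6 of 18 treatment wounds dropped. The treatment arm shows 30%, the control arm (12 × 0.30 + 6 × 0.10)/18 = 23.3%, a difference of +6.7 points. With 0% in affected pairs and 12 dropped (every Second- and Third-pair treatment wound), the control arm shows (6 × 0.30)/18 = 10% and the difference is +20.0. With equal closure in retained and affected pairs it is 0.

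**Maximum pain.** If the maximum is taken by arm, removing a wound can lower that arm's maximum or leave it unchanged; it cannot raise it.

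**The case against.** The strongest reply is that this is a secondary, descriptive matter. The primary and first secondary endpoints are untouched, SAP 6.1 rules out statistical testing, there are 6 subjects, and SAP 6.1.8 calls the comparisons exploratory. All of that stands and limits the consequence. It does not make the two percentages comparable.

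A second reply is that the mismatch would be visible. SAP 6.7.2 reports counts with percentages, which together normally reveal the denominator; SAP 6.2 summarises randomised wounds per subject, SAP 6.8.1 reports complete versus partial treatment, and the data are listed. This also stands: unequal denominators would usually show. The closure outcomes of the excluded wounds would not show in the table itself.

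A third is that Protocol 8.3.1.2 makes the number of pairs depend partly on the size of the largest wound in the pair, so shortage may be rarer than the area thresholds suggest. That is fair, and the frequency remains unknown.

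Some stronger readings should be resisted.
- A reader might infer that 6.4.2 already promises as-randomised handling of these wounds. Its wording, "will consider this wound in the SOC group (as randomized) as per the intent-to-treat philosophy", is limited to control wounds injected by mistake, in the primary analysis.
- A reader might infer that the rule contradicts the Protocol, where "The FAS population includes subjects who were administered FCX-007". That defines a set of subjects, not wounds, and Protocol 10.4 makes the SAP operative where the two differ.
- A reader might infer that the exclusion flatters the treatment. Wounds that go untreated may heal worse, but Protocol 8.3.1.2 allows later-pair wounds to have been open for a shorter time; the sign for closure is not determined.
- A reader might treat the pain effect as certain. SAP 6.7.3 could mean one pooled maximum over treated and control wounds, in which case there is no contrast between arms.

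**Conclusion.** The concern holds as a limited one. Followed as written, SAP 6.4.2 makes a post-randomisation exclusion in one arm and can leave the all-wounds closure percentages resting on different pairs. No planned analysis covers this: SAP 6.7.5 deals with missing assessments, not wounds that were assessed and then excluded, and the intent-to-treat sensitivity analysis in Protocol 10.5 concerns First Wound Pairs.

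The size is an illustration only. With 18 wounds per arm, 10% closure and no effect, dropping 1 to 6 treatment wounds shifts the difference by about −2.5 to +5.0 points; other assumed rates give 0 to +20.0. One wound is 1/18 = 5.6 points, or 1/12 = 8.3 points. It would be wrong to conclude that the shift always stays below one wound: with 12 per arm, 6 dropped and none of them closing, it is 1.20/6 − 0.10 = +10 points. The result of 0 after dropping whole pairs rests on shared prognosis within pairs.

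**What to change.** State in SAP 6.4.2 that when a Second- or Third-pair treatment wound is excluded, its paired control is excluded from the same timepoint in every all-wounds summary, including any maximum pain score computed by arm.

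Whole-pair exclusion restores comparability but still describes only pairs whose treatment wound could be fully treated. So add one descriptive summary of all randomised wounds in FAS subjects, as randomised, showing wounds per arm and the number not fully treated, by reason. Which of the two summaries leads is the sponsor's choice; the documents do not settle it. List the rule in SAP section 8.

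The cost is SAP wording and one extra table; completeness of treatment is already to be summarised under SAP 6.8.1. A few control wounds leave the fully-treated summary, and in the as-randomised table wounds that received little or no product count as treated.

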9.7. INVESTIGATIONAL PRODUCT ADMINISTRATION

Subjects will receive intradermal injections of FCX-007 into the superficial papillary dermis in each specified treatment wound in two or more treatment sessions. Intradermal injections of FCX-007 0.25 mL will be administered at approximately 1 cm intervals around, and within 1 cm of, the perimeter of the treatment wound(s) and across the wound (or healed wound bed, when applicable) (refer to Figure 4 and Figure 5); a maximum of 15 mL (in 60 injections) may be administered per session, and the Investigator is encouraged to administer the full quantity of FCX-007 should the total wound size permit. As the wound size and shape will dictate the quantity of FCX-007 to be administered, it is not possible to calculate this until after randomization. As a general rule, the maximum number of injections of FCX-007 is expected to be used over a surface area of approximately 60- 80 cm².

- * If possible, each treatment wound will receive the same amount and number of injections of FCX-007 during each of the first 2 treatment sessions (e.g., treatment wound labeled T1B receives 4.5 mL of FCX-007 in 18 injections at Day 1 (Visit 2) and at Week 12/Month 3 (Visit 3)). This may not be possible if a wound has expanded in size or under other clinical circumstances.

The first treatment session occurs at Day 1 (Visit 2) and the second at Week 12/Month 3 (Visit 3). At these visits, the treatment wound in the First Pair will be injected first, followed sequentially by the Second and Third Pairs (if applicable, and only as sufficient product is available). It is permissible for a treatment wound in the Second or Third Pair to be partially treated due to insufficient quantity of product, if the treatment wound in the First or Second Pair was completely treated.

At selected sites only, in a subset of subjects that consent to additional research skin biopsy collection, an additional single treated wound (not from a target wound pair) may be injected with FCX-007 at Day 1 (Visit 2) and Week 12/Month 3 (Visit 3) only.

Additional treatment sessions may occur at Week 24/Month 6 (Visit 4) and Week 36/Month 9 (Visit 5) when unclosed treatment wounds may be re-treated, and unclosed control wounds may be treated.

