Administration of FCX-007 will not occur in a specific treated wound if: 1) a treated wound shows unusual inflammation (beyond temporary inflammation 1-2 days post-injection) suspected to be related to the IP, based upon the Investigator's judgment; or 2) an area injected with IP shows unusual growth.

Subjects will be administered anesthesia per standard of care at the investigative site. To minimize pain and discomfort during the IP administration, the Investigator should determine the most appropriate anesthetic for each subject, including the use of topical anesthetic cream, local anesthesia, conscious (moderate) sedation, general anesthesia (if undergoing another procedure at time of injection) or a combination thereof. In addition, medication should be considered during and after the injections to treat pain and/or anxiety (e.g., lorazepam).

[figure not shown]
Refer to Appendix 3 for detailed instructions regarding the administration of IP.

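### The all-wounds Week 24 count drops Second- and Third-Pair treated wounds not fully injected at Week 12, a post-randomisation trigger that can depend on the wound's own response

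*SAP*

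**What the plan says.** The rule is in SAP 6.4.2. If treated wounds from the Second or Third Pair are "not able to be fully treated for any reason, then these wounds will not be included in efficacy analyses beyond the timepoint" concerned, which the SAP gives as Day 1 or Week 12. The Week 12 closure reading is taken before the Week 12 injection (Protocol 8.3.1.3), so a wound incompletely injected at that visit keeps its Week 12 result and is absent from Week 24 onward. The rule names treated wounds only. It does not mention their paired controls, and it does not apply to the First Pair.

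The endpoint most directly affected is "Complete wound closure of all wounds at Week 24" (SAP 5.1.2), reported as counts and percentages by treatment group (SAP 6.7.2). Because the rule covers efficacy analyses in general, it also reaches the all-wounds durability and pain summaries in SAP 6.7.3.

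Protocol 9.7 describes how injection can fall short or differ between sessions:

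- Shortage: "It is permissible for a treatment wound in the Second or Third Pair to be partially treated due to insufficient quantity of product". Product is capped at 15 mL per session and the First Pair is injected first.
- Withheld injection: a wound is not injected if "a treated wound shows unusual inflammation (beyond temporary inflammation 1-2 days post-injection) suspected to be related to the IP", or if the injected area shows unusual growth.
- Repeating the Day 1 number of injections at Week 12: "This may not be possible if a wound has expanded in size or under other clinical circumstances".

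**The concern.** An exclusion fixed at Day 1 precedes any response. An exclusion fixed at Week 12 follows twelve weeks of response and can depend on it. The trigger is also lopsided. Protocol 4.2.2 gives the second administration whatever the state of healing, and Protocol 9.7 covers injection across a healed bed, so doing well is no barrier to full treatment. Reacting to the product is a barrier, and enlarging may be one.

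The excluded data may well exist. Under Protocol 7.6.2, stopping administration does not stop assessments, so blinded Week 22 and Week 24 readings can be on file for a wound that the SAP leaves out. The sensitivity analysis in SAP 6.7.5 counts missing Week 24 readings as failures; it does not restore wounds that were assessed and then excluded.

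At stake is the treated closure percentage for all wounds. With formal testing removed (SAP 8), the percentages are the whole result for this endpoint, so their denominators matter. The protocol's own descriptions of the FAS and the secondary analyses (10.3.1, 10.4.2.2) contain no such wound exclusion, and SAP 8 does not list it as a change.

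**Working it through.** **The plan's own figures.** The plan gives no figure for how many wounds the rule will remove, so there is none to reproduce on this point. Its stated 85% power (24 pairs, 60% against 10% closure, 70% discordant) does reproduce, at 85.1% by the two-sided exact McNemar test. It concerns the First Pair and does not bear on this point.

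**Step 1: can the trigger depend on response?**

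| Route to incomplete Week 12 treatment | Source | Linked to that wound's response? |
|---|---|---|
| Suspected product-related inflammation | Protocol 9.7, stated | Yes, though it is a safety hold and not a finding of non-closure |
| Unusual growth at the injected area | Protocol 9.7, stated | Yes, same caveat; it is a different finding from an enlarging wound |
| The wound has enlarged and product runs out | Inference from the 15 mL cap and First-Pair priority | Yes |
| An earlier-pair wound uses the product, or supply is short | Protocol 9.7 | No |

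The cap can bind. Protocol 9.7 expects the maximum number of injections to cover about 60–80 cm², while three treatment wounds may total up to 3 × 50 = 150 cm².

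**Step 2: how many wounds are in play?** SAP 7 gives 6 enrolled subjects and SAP 4.1 up to three pairs each. That is at most 6 × 3 = 18 treated wounds, of which 6 × 2 = 12 are Second or Third Pair and subject to the rule.

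**Step 3: size, on assumed counts.** Take all 18 pairs, with 9 treated and 2 control wounds closed at Week 24. The difference is (treated closed ÷ treated counted) − (control closed ÷ control counted).

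| Wounds dropped | Treated only (literal rule) | With paired open controls |
|---|---|---|
| None | 9/18 − 2/18 = 38.9 points | 38.9 points |
| 2 open treated | 9/16 − 2/18 = 45.1 | 9/16 − 2/16 = 43.8 |
| 4 open treated | 9/14 − 2/18 = 53.2 | 9/14 − 2/14 = 50.0 |
| 2 closed treated | 7/16 − 2/18 = 32.6 | 7/16 − 2/16 = 31.3 |

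Removing the control as well reduces the shift but does not cure it, because the lost pair is still one selected on how its treated wound fared.

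**Step 4: the same effect at about the planned closure rate.** With 11 of 18 treated wounds closed (61.1%, near the assumed 60%), excluding one open wound gives 11/17 = 64.7%, and excluding four gives 11/14 = 78.6%.

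**The case against.** The case for leaving the rule alone has real content.

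- **Shortage is the only reason the protocol names for partial treatment of later pairs.** It can arise from the First-Pair wound and have nothing to do with the excluded wound. Because healed wounds are injected too, a closed wound can be excluded, and the difference then falls (last row of the table in Step 3). This stands, and it is why the direction is probable and not certain.
- **The protocol does not say that an enlarged wound cannot be fully treated.** A reader might infer this from the sentence about expansion, but that sentence qualifies giving the same number of injections at both sessions. An enlarged wound can receive more injections if product suffices. The link to exclusion runs through the cap and the injection order. This stands.
- **Inflammation and unusual growth are not treatment failure.** Such a wound may still close by Week 24. This stands.
- **There is no direct contradiction with the as-randomised sentence in SAP 6.4.2.** A reader might see one, because a control wound injected by mistake is kept: the primary analysis "will consider this wound in the SOC group (as randomized) as per the intent-to-treat philosophy". That sentence is limited to the primary efficacy analysis and to a different event. The contrast in approach is fair comment, but the documents do not support calling it an inconsistency.
- **The consequences are limited.** Nothing will be tested (SAP 6.1), complete or partial treatment is summarised (SAP 6.8.1), and data from all visits are listed (SAP 6.1.3). A careful reader could largely rebuild the full count. This lowers the stakes but leaves the reported percentage unchanged.

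**Conclusion.** The point holds in a limited form. SAP 6.4.2 lets an event after randomisation, sometimes caused by the wound's own response, decide whether that wound counts at Week 24. The likely effect favours FCX-007, because reacting or enlarging can prevent full injection and healing does not.

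A reader might go further and conclude that the rule systematically removes treatment failures. The documents do not support that: they give neither the number of affected wounds nor their outcomes, and shortage can remove closed wounds as well.

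The First Pair, and so the primary endpoint, is untouched, and no type I error is at issue. On the assumed counts the difference moves from 38.9 points to between 31.3 and 53.2, depending on which wounds leave and whether their controls go too. That range assumes three pairs in all 6 subjects, 9 treated and 2 control closures, and two or four exclusions. With fewer pairs, each exclusion would weigh more.

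**What to change.** Change SAP 6.4.2 as follows.

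1. Keep every wound fully treated at Day 1 in the Week 24 all-wounds count, as randomised, whatever happened at Week 12. Use the same set for the later all-wounds durability and pain summaries.
2. Limit exclusion to Second- and Third-Pair wounds not fully treated at Day 1, for any reason arising before a post-treatment reading, and remove the paired control with them.
3. Report the subset fully treated at both sessions, with its paired controls, as a supportive row.
4. List each incomplete Week 12 treatment with its reason and the wound's Week 24 status.

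The cost is a sentence or two in the SAP, one table row and a short listing. The downside is that the headline rate will include wounds with an incomplete second session and may be slightly lower. No dosing or administration rule changes.
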